Most women who have a preterm birth display a shortened neck for the first time approximately between 18-22 weeks of gestation, so the initial examination should be conducted at least within that period. Besides the already established inverse relationship between CL and the risk of preterm birth, the earlier the cervix is shortened during gestation, the higher the likelihood of a preterm birth. In women at higher risk, a CL <25 mm has a positive predictive value of 70% for preterm birth before 35 weeks when detected at 14-18 weeks, and 40% when detected at 18-22 weeks (5). In the same line of evidence, Vaisbuch *et al.* (4) recently demonstrated an approximate two-fold risk of delivery before 28 or 32 weeks if CL is  $\leq 15$  mm before 20 weeks (76.9% and 80.8%) versus 20-24 weeks (30.9% and 48.1%). Overall, this evidence suggests that starting the screening of patients with cervix measurements earlier than week 18 and using a 25-mm CL limit to determine the need for an intervention as discussed in this clinical study might entail a greater advantage.

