### **3 STUDY OBJECTIVES**

**Primary Objective:** This is a Phase II clinical study to assess the efficacy of two cerclage pessaries containing 6.3 g and 7.7 g of sustained-release micronized progesterone for the prevention of preterm birth, established by spontaneous delivery before gestation weeks 32 (31 6/7) and 34 (33 6/7) when the pessary is inserted between weeks 16 and 24 and removed in gestation week 36 6/7, in pregnant women at risk of preterm birth.

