## **9 STATISTICS**

This project aims to conduct a randomized, open-label, controlled, clinical-exploratory phase II study evaluating the efficacy of a cerclage pessary containing one of 2 doses of sustained-release micronized progesterone for prevention of preterm birth, compared to the treatment method currently used by obstetrics-gynecology specialists, which comprises the administration of one daily capsule by vaginal route of 200 mg of progesterone. A total of

270 pregnant participants at risk of preterm birth will be enrolled, screened, and randomized to the 3 groups of treatment previously described. The number of patients listed ( $n = 270$ ) refers to the number of patients who effectively are enrolled and successfully complete the study. Therefore, an enrollment of at least 10% over that number (27 patients or more) should be considered due to the eventual withdrawal or early loss to follow-up of patients initially recruited.

As primary results, the proportions of spontaneous preterm delivery before gestation weeks 32 and 34 will be compared between the control group and the 2 groups with the pessaries containing different doses of progesterone. The risk of spontaneous preterm birth from the time of inclusion in the study through the gestation weeks 32 and 34 will be determined by a Kaplan-Meier analysis, where gestational age will be the time scale and spontaneous delivery will be the event; elective parturitions will be censored. For the purpose of this analysis, pregnancies will no longer be considered as high risk for the event if delivery occurs at the week of gestation 34 (34 0/7) or beyond.

As secondary outcomes, those qualitative variables in pregnant participants at risk of preterm birth will be evaluated, and the percentage distribution of acceptability responses or side effects recorded will be determined. For the quantitative variables (measurements of length and cervical angulation), the averages and standard deviations of the values found will be compared. Accordingly, each participant will work as her own control.

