2. OBJECTIVES

PRIMARY

To evaluate the efficacy of two cerclage pessaries containing 6,3 g and 7,7 g of micronized progesterone of sustained release, in the prevention of premature birth, established through spontaneous delivery after 32 weeks but before 34 weeks of gestation, when the pessary is inserted between week 16 and 24, and removed at 36 6/7 weeks of gestation in pregnant women at risk of premature birth.

SPECIFICS

- Record the occurrence of premature rupture of membranes before weeks 32 and 34 weeks of gestation.
- Evaluation of anatomical characteristics of the cervix in pregnant women: position and length.
- Establish the acceptability and tolerance in pregnant women, with the use of the cerclage pessary.
- Evaluation of local and systemic safety in pregnant women, with the use of the cerclage pessary.

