The sample size calculation is based on the power to detect differences in the proportion of spontaneous birth between 32 and 34 weeks of gestation, between the formulations of cerclage pessaries with respect to the control group (vaginal progesterone 200 mg capsules). Data collected of at least 90 women in each group will provide at least 80% of the power to detect differences with a rate of 40% or more, using a test of Chi-square of two tails with $\alpha = 0.05$ without correction.

We estimate that up to 10% of the enrolled women may not complete the study, so it must be planned to enroll at least 99 pregnant women in each group to reach at least 198 treated subjects with cerclage pessary and 99 subjects treated with soft capsules of progesterone as a control group (i.e. 99 per each vaginal formulation).

RANDOMIZATION

The randomization will be generated by an independent statistician. The program will be linked in sequential numbers with the code of randomized treatment. A qualified staff member of ANDROMACO laboratory will keep randomization codification, until the database is clean and ready for analysis. The treatment will be dispensed according to the randomization code, the women with unique pregnancy enrolled, will be randomized to receive one of the vaginal formulations of the study.

For the next volunteer, the site will have the next randomization number available. Each woman will receive only the formulation corresponding to the randomization number. The Investigator will record on the log the randomization number and the printed code on each formulation container. Each sites coordinator will assign the randomization code to the volunteers.

Subjects will be randomized to the following three study groups:

- Control Group (A): Intravaginal capsule of micronized progesterone 200 mg on a daily basis.
- Pessary Group (B): Pessary with 6.3 g of sustained release progesterone for a period of around 4 to 5 months.
- Pessary Group (C): Pessary with 7.7 g of sustained release progesterone for a period of around 4 to 5 months.

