4. DOCUMENTS AND CHANGE OF VERSIONS

Version #	Date of Review	Date of Approval	Reason for Change
1.0	05Apr2017		N/A
2.0	21Apr2017		Additions to different sections
3.0	12May2017		English Version and clarification of some issues

CHANGES IN THE PLAN

At the moment there are no changes to the protocol or in the conduction of the study.

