10. EFFICACY ANALYSIS

STATISTICAL HYPOTHESIS

Null Hypothesis:

There is no difference between the methods of cerclage pessaries with a sustained release of 6.3 and 7.7 g of progesterone (Treatments B and C, respectively) with respect to the control method (Treatment A) for at least 20 weeks.

Alternative Hypothesis:

There is a difference between the Control Method (Treatment A) with respect to the one of cerclage pessaries with a sustained release of 6.3 and 7.3 of progesterone for a period of 4 to 5 months.

“There is a difference between the methods of cerclage pessaries with a sustained release of 6.3 and 7.3 g of progesterone (Treatments B and C respectively) with respect to the Control Method (Treatment A) for a period of 4 to 5 months”.

PRIMARY ANALYSIS

The primary objective is to evaluate the efficacy of two cerclage pessaries with doses of 6.3 and 7.7 g of sustained release micronized progesterone with respect to the standard treatment of 200 mg of progesterone in capsules administered daily. The primary efficacy analysis will be assessed by comparing the proportions of spontaneous premature delivery after 32 weeks but before 34 weeks of gestation, as primary results, among treatments through the CMH test. Also, the odds ratio and 95% confidence interval will be estimated, considering Group A as the control to be compared with groups B and C. Secondly, the comparison of proportions between the groups C and A will be done with the intention to confirm the significant difference between the highest dose and the standard treatment. Afterwards, the same comparison of proportions will be done with treatment B in order to establish the difference between the group of a minor dose and the standard. Finally the comparison between treatment B and C will be done hoping to demonstrate there is a difference of superiority between B and C where C must be minor than B regarding the number of low-risk pregnancies. The transitivity between treatments will be established according to the results. This is expected to be as follows:

$$\textit{Treatment C} < \textit{Treatment B} < \textit{Treatment A}$$

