Occurrence of membranes' ruptures: Premature rupture of membranes after 32 weeks but before 34 weeks of gestation. The Cochran-Mantel-Haenszel (CMH) test will be used, where the incidence of rupture of membranes in each group will be compared and will be identified through the registration of adverse events.

Anatomical cervical changes (Only groups B and C): The length of the cervix and cervical angle variables, will be described as continuous and measured variables through time, using the test of comparison of means through the Analysis of Variance (ANOVA) for repeated measures, considering the baseline result as a covariate in the comparison and shall be based on the sum of squares type III. The difference between groups regarding the change from baseline will be assessed through t tests paired within ANOVA, utilizing the difference in means estimated by least squares. These comparisons will be made amongst all treatment groups with pessary.

Acceptability and tolerability of insertion (only groups B and C):

Acceptability and tolerability will be assessed through a questionnaire which must be completed at the beginning and end of the study. Questions (i) and (ii) are answered at visit 1, question iii (VAS) is answered at visit 1 and final visit, and questions (iv) to (ix) are answered at the final visit.

It is composed of several items

- (i) Ease of insertion (visit 1). This question has the following categories: 1 = very good, 2 = good, 3 = regular, 4 = bad and 5 = very bad; and only one of them will be selected.
- (ii) Subjects pain at the time of insertion (visit 1). This question has the following categories: 1 = without pain, 2 = with little pain, 3 = with moderate pain, 4 = with intense pain and 5 = with unbearable pain; and only one of them will be selected.

- (iii) Visual Analog Scale of pain (VAS) (visit 1 and final visit): this scale is evaluated in 10 points where 10 represents the worst pain suffered during her lifetime and 1 the absence of pain.

Analysis for the VAS will be described as continuous and measured variables through time using the test of comparison of means through the Analysis of Variance (ANOVA) and must be based on the sum of squares type III. The treatment differences regarding the change from baseline, will be assessed through t tests paired within ANOVA, utilizing the difference in means estimated by least squares. These comparisons will be made amongst all treatment groups.

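### The SAP replaces the protocol's primary endpoint (spontaneous birth before 32 and before 34 weeks) with births between 32 and 34 weeks only, so births before 32 weeks become non-events

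*SAP*

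**What the plan says.** **Protocol.** Section 9 states that "the proportions of spontaneous preterm delivery before gestation weeks 32 and 34 will be compared between the control group and the 2 groups". The synopsis and section 3 give the cuts in days, 31 6/7 and 33 6/7 weeks. Sections 7.1 and 9.1 also use births before 32 and before 34 weeks. Each cut counts every spontaneous birth from inclusion up to that point.

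**SAP.** The endpoint is a two-week band in five places:

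- Section 2, primary objective: "established through spontaneous delivery after 32 weeks but before 34 weeks of gestation".
- Section 3, sample size: "differences in the proportion of spontaneous birth between 32 and 34 weeks of gestation".
- Section 10, primary analysis: "comparing the proportions of spontaneous premature delivery after 32 weeks but before 34 weeks of gestation, as primary results".
- Section 10, the statement a few lines later on how the effective response is determined, which repeats the band.
- Section 10, secondary analysis: "Premature rupture of membranes after 32 weeks but before 34 weeks of gestation".

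Elsewhere the SAP keeps the cumulative form. Its section 2 list of specific objectives has membrane rupture before weeks 32 and 34. Its Kaplan-Meier analysis runs from inclusion to weeks 32 and 34. Section 4 says "At the moment there are no changes to the protocol or in the conduction of the study".

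**The concern.** A band of 32 to 34 weeks does not measure prevention of preterm birth. A treatment that postpones a birth from 30 to 33 weeks adds an event. A treatment that brings a birth forward from 33 to 30 weeks removes one. The births left out are the ones that matter most clinically: protocol section 2 attributes neonatal morbidity and mortality mainly to births before 32 weeks. The primary outcome is also meant to identify the effective pessary dose, so a comparison that can point the wrong way bears directly on the trial's main decision.

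**Working it through.** **Step 1. How a birth before 32 weeks is handled.** The SAP compares proportions and states no exclusion for such births. Section 6 makes the per-protocol set the main efficacy set and keeps women who completed their visits or were followed to the end of pregnancy. A woman who delivers spontaneously at 26 weeks is therefore in the denominator, and she is not in the numerator because 26 weeks lies outside the band. If she were excluded instead, the comparison would be conditional on an outcome after randomisation, which also departs from the protocol.

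**Step 2. Can the direction reverse?** OR = [p1/(1 − p1)] / [p0/(1 − p0)], with p0 control and p1 pessary. The rates are assumed. Control: 12% before 32 weeks and 8% at 32 to 34, so 20% before 34.

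| Scenario | Before 32 | Before 34 | 32 to 34 only (SAP) |
|---|---|---|---|
| (a) pessary 6% before 32, 10% in band | (0.06/0.94)/(0.12/0.88) = 0.47 | (0.16/0.84)/(0.20/0.80) = 0.76 | (0.10/0.90)/(0.08/0.92) = 1.28 |
| (b) pessary 16% before 32, 4% in band | (0.16/0.84)/(0.12/0.88) = 1.40 | (0.20/0.80)/(0.20/0.80) = 1.00 | (0.04/0.96)/(0.08/0.92) = 0.48 |

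In (a) a benefit looks like harm. In (b) an excess of very early births looks like benefit.

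The same in invented counts, 90 per arm, uncorrected chi-square. Control has 18 births before 32 weeks and 9 in the band; pessary has 6 and 12.

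- Before 32: 18 v 6, OR 0.29, p = 0.009.
- Before 34: 27 v 18, OR 0.58, p = 0.12.
- SAP band: 9 v 12, OR 1.38, p = 0.49.

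A clear reduction in births before 32 weeks is invisible to the primary test.

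**Step 3. The plan's own sample size.** Both documents claim at least 80% power with 90 per group for a difference of 40%, two-sided 0.05, uncorrected chi-square. They give no control rate, so the figure cannot be reproduced. If 40% is a relative reduction, 80% power at n = 90 needs a control rate of about 51% (51% v 30.6%).

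**Step 4. Power lost to the band.** Assume a uniform 40% relative reduction and n = 90 per arm. With p̄ the mean of the two rates,

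power = Φ{ [ |p0 − p1|√n − 1.96√(2p̄(1 − p̄)) ] / √[p0(1 − p0) + p1(1 − p1)] }.

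At a 20% control rate before 34 weeks with 40% of those births in the band:

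- Before 34, 20% v 12%: (0.759 − 1.016)/0.515 = −0.50, power 31%.
- Band, 8% v 4.8%: (0.304 − 0.678)/0.345 = −1.09, power 14%.

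Over a range of band shares:

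| Control rate before 34 | Power, before 34 | Power, band (share 30%) | (share 40%) | (share 70%) |
|---|---|---|---|---|
| 20% | 31% | 11% | 14% | 22% |
| 30% | 47% | 15% | 19% | 32% |
| 51% | 80% | 24% | not run | 57% |

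**Step 5. Where early births fall.** Protocol section 2 cites a short-cervix series with 80.8% delivered before 32 weeks when detected before 20 weeks, and 48.1% when detected at 20 to 24 weeks. It gives no figure before 34 weeks. In the second group, the band could hold at least half of births before 34 weeks only if 2 × 48.1% = 96.2% or more delivered before 34. That series is limited to cervical length of 15 mm or less, so it is background for this trial's wider population, not an estimate.

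**The case against.** The best defence is that this is a drafting or translation slip. SAP section 1 calls its design overview a summary and names the protocol as the governing document. Section 4 describes version 3.0 as the English version. The SAP also keeps the cumulative wording in one specific objective and in the Kaplan-Meier analysis, so very early births would still appear in the report.

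This shows which definition was probably intended, but it does not repair the primary test. The band is written into the objective, the sample size and the primary analysis, and the SAP labels the Kaplan-Meier analysis exploratory. The cumulative passages make the SAP inconsistent with itself.

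Four limits do stand:

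- The SAP never says that births before 32 weeks are successes. That follows from reading its definition literally.
- The odds ratios above are point estimates. With 90 per arm, scenario (a) is about 7 v 9 events (p about 0.60) and (b) about 7 v 4 (p about 0.35). They show that the direction can reverse, not that a wrong conclusion would reach significance.
- At control rates of 20% or 30%, the protocol endpoint is itself far below 80% power. That shortfall is a separate sample-size matter; only the further drop belongs here.
- The section 4 statement concerns changes to the protocol and its conduct. It is weaker than an assurance that the analyses match, though it does mean that no departure is disclosed.

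**Conclusion.** The concern holds, and the SAP should be corrected before the primary analysis is programmed. The two documents define different primary endpoints. The SAP's version, taken literally, counts the most serious preterm births as non-events. This conclusion rests on the text alone.

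The size is illustrative because the documents give neither a control rate nor the split of births around 32 weeks. Under the assumed rates, an odds ratio of 0.76 before 34 weeks becomes 1.28, and one of 1.00 becomes 0.48. If 30% to 70% of births before 34 weeks fall in the band, power for a uniform 40% relative reduction drops from 31% to 11–22% at a 20% control rate, and from 47% to 15–32% at 30%.

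**What to change.** In SAP section 2 (primary objective), section 3 (sample size) and section 10 (primary analysis, the effective-response statement and membrane rupture), replace the 32-to-34-week band with two cumulative endpoints: before 32 0/7 weeks (up to 31 6/7) and before 34 0/7 weeks (up to 33 6/7). For delivery, say explicitly that every spontaneous birth earlier than the cut is an event. For membrane rupture, say the same of every rupture earlier than the cut. The Kaplan-Meier text already has the cumulative form.

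The cost is a revision of SAP wording. No new data are needed, since gestational age at birth is collected at the final visit (SAP Table 1, footnote 4).

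Neither document says how the two cuts are ordered for testing. That is a separate multiplicity question, but the same revision is a convenient place to settle it.

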5. ANALYSIS CONVENTIONS

The statistical analysis will be made by ILS Clinical Research under the authorization of Laboratorio Andromaco S.A.

GENERAL PRINCIPLES

The statistical analysis will be provided to give a general summary of the study subjects and a vision of the efficacy and safety of the results. The data provided by the sites will be summarized for this purpose. Tables of absolute and relative frequencies will be constructed for the quality variables. All the percentages will be presented with a decimal. The quantitative variables will be summarized with the number of subjects participating (n), mean, standard deviation (SD), and median, maximal and minimal.

Two tailed test will be carried out for all the analysis and the type I error is 0.05 for continuous variables and the discrete variables. All p values shall be rounded to three decimal and the values under 0.001 will be presented as <0.001 and values greater than 0.999 will be presented as 1.000. A comparison of the treatment groups will be done with respect to the demographic and baseline characteristics using inferential statistical techniques to detect if any of these variables may condition the results in the dependent variables. Comparisons in qualitative variables will be carried out using the Cochran-Mantel-Haenszel (CMH) test of general association, while the comparisons in quantitative variables will be made with a test of comparison of means (ANOVA analysis of variance) for independent samples with normal distribution. In the cases of no normality on the continuous variables, or in case of not belonging to the exponential family for discrete data, the parametric tests will be replaced for nonparametric tests such as Kruskal-Wallis or Friedman. These tests will be presented in each table as deemed necessary. All confidence intervals will be two-tailed and at 95%.

Table 1: Study Schedule of Assessments

Activities	Visit 1	Visit 2	Visit 3	Visit 4	Visit 5	Visit 6	Visit 7	Final Visit
Demography	X							
Medical History	X							
Physical Exam	X	X	X	X	X	X	X	X
Gynecological Exam	X							
Vital Signs	X	X ¹	X ¹	X ¹	X ¹	X ¹	X ¹	X ¹
Transvaginal Ultrasound	X	X ²	X	X	X	X	X	X
Pre-birth Control	X							
Obstetric Background	X							
Lab Tests (Blood and Urine)	X							
Eligibility	X							
Vaginal Discharge	X	X ³	X ³	X ³	X ³	X ³	X ³	X ³
Randomization	X							
Pessary Insertion	X							
Acceptability and tolerance to the insertion	X							X
Concomitant Medications	X	X	X	X	X	X	X	X

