8. DEMOGRAPHY AND POPULATION CHARACTERISTICS

Baseline characteristics and demographics will be summarized for PP and ITT population defined in section 2.3.1

Categorical variables will be summarized in tables of frequencies and percentages. Continuous variables will be described by mean, standard deviation, median, max and min.

They will be compared by treatment. For continuous variables a variance analysis (ANOVA) will be used for means comparison for independent samples. Categorical variables will be compared through the test of χ^2 Cochran-Mantel-Haenszel.

Demographic characteristics included age (years), race, weight, height and Body Mass Index (BMI).

MEDICAL HISTORY

The medical history refers to whether the subject presents or presented any relevant conditions (Yes/No), a summary of conditions, diseases or surgical procedures and if these are still active or not. The data will be summarized in tables of frequencies and percentages based on the total number of subjects included in each treatment group and will only be handled for informatory purposes.

PHYSICAL EXAM

The physical exam includes examining body parts such as the abdomen, gallbladder, cardiovascular, endocrine, gastrointestinal and immune system, muscle-skeletal, neurological, psychiatric, respiratory, limbs, head, nose, eyes, ears, lymph nodes and allergies, nutritional facts, scars, skin, thyroid, etc. This will be evaluated in detail at baseline and documented in each visit just if there exist clinical relevance. The information will be summarized in tables of frequencies and percentages based on the total number of subjects in each treatment group and will only be handled for informatory purposes.

VITAL SIGNS

Vital signs consider values of systolic and diastolic blood pressure, heart rate, pulse and temperature. These shall be reviewed as part of the physical examination and the information will be presented in every visit. The information will be summarized in tables with number of participating subjects (n), mean, standard deviation (SD), median, max and min and will only be handled for informatory purposes.

GYNECOLOGICAL EXAM

The gynecological exam includes examination of breasts, external genitalia, vagina, cervix, uterus, other abnormalities, etc. The information will be summarized in tables of frequencies and percentages based on the total number of subjects in each treatment group and will only be handled for informatory purposes.

OBSTETRIC HISTORY

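### The primary CMH test names no stratum and leaves obstetric history and cervical length unused; stratifying by these entry factors is a cheap improvement

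*SAP*

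**What the plan says.** The primary analysis in SAP section 10 rests on "comparing the proportions of spontaneous premature delivery after 32 weeks but before 34 weeks of gestation", tested "as primary results, among treatments through the CMH test". An odds ratio with 95% CI follows for B and C against A, and the SAP does not say whether it is crude or stratified. No stratum is named there or wherever else the test appears:

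- SAP section 5: "Comparisons in qualitative variables will be carried out using the Cochran-Mantel-Haenszel (CMH) test of general association".
- SAP section 8: "Categorical variables will be compared through the test of" CMH type.
- SAP section 10, membrane rupture: "The Cochran-Mantel-Haenszel (CMH) test will be used, where the incidence of rupture of membranes in each group will be compared". The vaginal discharge analysis uses a generalized CMH test, also without strata.

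Neither Protocol 5.3 nor the SAP's randomization text describes stratified allocation. The sample size is set to "detect differences with a rate of 40% or more, using a test of Chi-square of two tails", without strata.

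SAP section 5 also plans baseline comparisons "using inferential statistical techniques to detect if any of these variables may condition the results in the dependent variables", and does not say what follows from a positive result. SAP section 8 limits obstetric history to an informational role. A secondary analysis in section 10, of cervical change, does adjust for baseline: "considering the baseline result as a covariate in the comparison".

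**The concern.** Women enter by one of two routes, restated in SAP section 10: a cervix of 10-25 mm without risk factors, or a cervix of at least 10 mm with a qualifying history. Protocol section 2 treats cervical length and prior risk as strong markers of preterm birth. Both are recorded at visit 1 (SAP Table 1: obstetric background and transvaginal ultrasound). The primary test ignores them, although CMH is built to use such factors.

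Two things are at stake. One is some precision, if the entry groups differ in risk. The other is that, in an open-label trial, a CMH test without stated strata can be completed later by site, history or cervical length. The baseline tests in SAP section 5 could prompt such a choice.

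**Working it through.** **1. The plan's own figure.** Both documents state 90 per group, at least 80% power, two-sided alpha 0.05, uncorrected chi-square, and differences at a rate of 40% or more. No control risk is given. With z = (|p1-p2|√n - 1.96√(2p̄q̄)) / √(p1q1+p2q2), 50% vs 30% gives (0.2×9.487 - 1.96×0.693)/0.678 = 0.796, so power is 78.7%. Read as a 40% relative reduction, 80% needs a control risk of about 51%; at 20% vs 12%, power is 30.9%. Read as 40 percentage points, power exceeds 99%. The figure cannot be reproduced without an assumption, so the powers below are illustrative.

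**2. The test as written.** With one stratum, CMH = Pearson chi-square × (N-1)/N. For two arms N = 180, so the factor is 179/180 = 0.994. This is in effect the planned chi-square.

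**3. The stratified test.** In stratum k, let a be the treated events, n1 and n0 the arm sizes, m the total events and N = n1 + n0. Then X² = [Σ(a - n1·m/N)]² / Σ[n1·n0·m(N-m)/(N²(N-1))], on 1 df.

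**4. Power, one pairwise test.** The simulation used 90 per arm and 300,000 trials per scenario. The cells are no history / history up to 25 mm / history over 25 mm, in an assumed mix of 50:25:25. All risks, effects and mixes are assumptions. Entries are unstratified → three cells, in percent.

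| Control risks | Odds ratio 0.4 | 40% relative reduction |
|---|---|---|
| 10/40/5% | 40.9 → 44.3 (+3.4) | 25.3 → 27.5 (+2.2) |
| 15/40/10% | 50.3 → 52.9 (+2.6) | 30.6 → 32.4 (+1.8) |
| 10/20/5% | 34.4 → 34.6 (+0.2) | 18.2 → 18.0 (-0.2) |
| 15% in all | 45.3 → 44.5 (-0.8) | 23.6 → 23.2 (-0.4) |
| 4/8/2% | 15.0 → 15.3 (+0.3) | 8.5 → 9.0 (+0.5) |
| 3/6/1% | 11.2 → 10.4 (-0.8) | 7.2 → 6.9 (-0.3) |
| 2/4/1% | 6.6 → 5.7 (-0.9) | 4.9 → 4.3 (-0.6) |

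The small gains at 4/8/2% reflect discreteness (type I error 4.2% unstratified, 4.8% stratified), not precision. The low-risk rows are relevant because the 32-34 week window in SAP section 10, taken literally, would leave few events. At odds ratio 0.4, two arms together have about 22 events at 10/40/5%, 6 at 4/8/2% and 4 at 3/6/1%.

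**5. A small over-25 mm cell.** Protocol 4.1 and SAP section 3 describe inviting women with 10-25 mm, so this cell may be small. With mix 50:45:5, 10/40/5% and odds ratio 0.4, power is 53.5 unstratified, 56.8 with the two history cells merged, and 57.8 with three cells (+4.3). With 15% in all cells it is 45.3, 44.7 and 44.3 (-1.0). Merging a 5% cell therefore costs about 1 point or less. Merging a 25% cell gives up about 3 points (41.3 vs 44.3 at 10/40/5%).

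**6. The steepest gradient the protocol suggests.** Protocol section 2 quotes a 70% predictive value for higher-risk women with a cervix under 25 mm, for birth before 35 weeks when detected at 14-18 weeks (40% at 18-22 weeks). At 20/70/10%, odds ratio 0.4, power goes from 49.3 to 60.4 (+11.1) with mix 50:25:25, and from 59.9 to 70.9 (+11.0) with 50:45:5. With a 40% relative reduction (50:25:25) it goes from 47.2 to 55.5 (+8.3).

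**7. Type I error.** Each version fixed in advance (none, four equal sites, history, three cells) rejects a true null in about 3.7-5.1% of trials. At least one of the four rejects in 7.5% at 10/40/5%, 5.9% at 15% in all, and 5.8% at 3/6/1%. With only no strata and site as options, the figure is 5.5% at 10/40/5%.

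**The case against.** The strongest reply is that the plan already has a workable default. Without strata, CMH is the chi-square used for the sample size. It serves throughout the SAP as the general test for categorical data, and no stratified randomization is being ignored. This stands: the test is valid as written, and a missing stratum would by itself be a matter of wording.

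A second reply is that SAP section 8 keeps obstetric history for information only, which weighs against using it as a stratum later. This also stands in part. Two of the four versions behind the 7.5% use history, and without the history-based versions the figure is 5.5%. Cervical length is not under that limit, however, and the purpose given for the baseline tests in SAP section 5 leaves the matter unclear.

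A third reply is that the gain depends on the chosen risks and the cell scheme is a matter of judgement. That is fair. Odds ratio 0.4 is not in the documents, no scenario in steps 4 and 5 reaches the stated 80% power, and the protocol's rationale separates 1-15 from 16-25 mm, which the three cells do not. A reader might infer from steps 4 and 5 that the gain can never exceed about 4 points, or from step 6 that it will be around 10. The documents support neither, because they give no risks or sizes for the entry groups.

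**Conclusion.** This is a cheap improvement to a valid test. Stratifying by the entry factors changes power by about -1 to +4 points under assumed cell risks up to 40%, and by about +8 to +11 points if the 70% figure applied. That figure is an upper anchor, because it concerns birth before 35 weeks after early detection. The result rests on 90 per arm, the assumed mixes, and an odds ratio of 0.4 or a 40% relative reduction.

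Fixing the strata also settles one primary test. A reader might infer that the plan's type I error is inflated to 7.5%. The documents do not support that. The figure assumes cell risks of 10/40/5% and that the most favourable of four versions is always picked; nothing says this would be done, and the SAP's limit on history makes it less likely. A steeper risk gradient would move the ceiling up somewhat, but it would remain a ceiling.

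**What to change.** In SAP section 10, before outcomes by arm are reviewed:

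- Pre-specify the overall, C vs A and B vs A CMH tests, stratified by no history (10-25 mm), history with cervical length up to 25 mm, and history with cervical length above 25 mm. Merge the two history cells if the last is very small, judged on counts pooled over arms.
- Use one definition of history for the strata. The Protocol Synopsis and 5.1 do not limit it to the last pregnancy, whereas Protocol 4.1.1 and 5.4.1 and SAP sections 8 and 10 do. These passages must be reconciled first.
- Amend the statement in SAP section 8 that history serves only for information.
- Report the Mantel-Haenszel odds ratio with 95% CI as the primary estimate, beside the crude one.
- State that the baseline tests in SAP section 5 will not be used to choose adjustment.

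The cost is SAP wording and a few lines of SAS, with no new data. The downsides are up to about 1 point of power lost if the factors are not prognostic or events are few, and an odds ratio that is conditional on the strata rather than marginal.
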